4.1.3.1.2 Onset and End Dates of Adverse Event

Incomplete AE onset and end dates will be imputed, respectively, as the earliest and latest possible date consistent with the partial date and assigned treatment period (pre-study, pre-treatment or ontreatment), where:

- Pre-study: The onset of the AE is on or after the CABENUVA treatment start date, but prior to enrollment in the study
- Post-enrollment, pre-treatment: The onset of the AE is prior to the on-study CABENUVA treatment start date

 Post-enrollment, on-treatment: The onset of the AE is on or after the on-study CABENUVA treatment start date

If the event start day is missing, assume the first day of the month. If the month or entire start date are missing, assume the event occurred on January 1 if the year of the start date is not the year of the CABENUVA treatment start. If the year of the start date is the year of CABENUVA treatment start, then the following imputation rules apply:

- If the stop date contains a full date and is earlier than the CABENUVA treatment start date, then the set start date = January 1
- Else, the set start date = the CABENUVA treatment start date

If the event end day is missing, assume the last day of the month. If the month or entire end date are missing, there will be no imputation.

Events that that begin on or after the date of on-study CABENUVA treatment initiation will be considered treatment-emergent events.

Note that if the AE end date is present, the imputed onset date will always be on or prior to the end date.

4.1.4 Power and Sample Size

The study sample size of up to 120 participants is based on the primary objective "To evaluate feasibility of CABENUVA administration at infusion centers/ASAs from participants" with an endpoint defined as "the proportion of participants that agree or completely agree (a score of 4 or higher) across all items on the Feasibility of Intervention Measure (FIM) at Month 8". Sample size calculations were not powered to evaluate clinical or safety outcomes.

4.2 Analysis Sets

4.2.1 Enrolled Set

"Enrolled" participants will include PLWHIV-1 who have agreed to participate in this clinical study, following the completion of the informed consent process, and have met the baseline eligibility criteria. If required, a legally acceptable representative may provide the participant's agreement to participate in the clinical study and sign the ICF.

The Enrolled Set will include all participants who provided a signed ICF, met the eligibility criteria, and were enrolled in the study. Some participants may meet the eligibility criteria but may not be enrolled for other reasons.

4.2.2 Safety Set

The Safety Set will consist of all participants in the Enrolled Set who received at least one on-study CABENUVA injection(s).

4.3 Disposition

4.3.1 Study Disposition

The study disposition will be summarized as the number and percentage of participants in each analysis set (i.e., Enrolled Set and Safety Set):

- Screen failed, and reason(s) such as:
 - AE
 - Did not meet inclusion/exclusion criteria
 - Referring physician decision and reason specified
 - Protocol deviation
 - Study terminated by sponsor
 - Withdrawal by participant and reason specified
- Met entry criteria but not enrolled
- Consented/reconsented, and enrolled
- Ongoing at the time of analysis
- Completed the study
- Discontinued treatment
 - AE
 - Lack of efficacy
 - Referring physician decision and reason specified
 - Protocol deviation
 - Sponsor terminated site
 - Sponsor terminated treatment
 - Study terminated by sponsor
 - Withdrawal by participant and reason specified
- Discontinued study
 - AE
 - Lack of efficacy
 - Referring physician decision and reason specified
 - Protocol deviation
 - Sponsor terminated site
 - Sponsor terminated treatment

- Study terminated by sponsor
- Withdrawal by participant and reason specified
- Lost to follow-up
 - Participant relocated
 - Participant incarcerated

A listing of all inclusion and exclusion criteria deviations will be provided for all participants in the Enrolled Set.

4.3.1.1 Lost to Follow-up

A participant will be considered lost to follow-up if they fail to return for one or more scheduled visits and is unable to be contacted by the IC/ASA or the HIV care provider.

The following actions must be taken if a participant fails to return to the IC/ASA for a required study visit:

- The IC/ASA must immediately contact the HIV care provider if a participant has missed a visit.
- The IC/ASA must attempt to contact the participant and reschedule the missed visit as soon as possible and counsel the participant on the importance of maintaining the assigned visit schedule and ascertain whether or not the participant wishes to and/or should continue receiving monthly or every-2-monthly injections at the IC/ASA.
- Before a participant is deemed lost to follow-up, the IC/ASA and HIV care provider must make every effort to regain contact with the participant. These contact attempts should be documented in the participant's medical record.
- Should the participant continue to be unreachable, they will be considered to have withdrawn from the study with a primary reason of "Lost to Follow-up."

4.3.2 Protocol Deviations

Protocol deviations will be recorded within the Clinical Trial Management System and undergo cross-functional team review prior to final database lock (DBL). The Study Deviation Rules Document contains all potential protocol deviations, classified by Clinical Trial Management System subtype (see Section 7.2).

Important protocol deviations can be related to study eligibility criteria, study conduct, participant management, or participant assessments. Prior to DBL, important protocol deviations will be identified and documented based on a review of potential protocol deviations. The potential protocol deviations will be identified through programmatic checks of study data, as well as through review of selected data listings.

Protocol deviations may include the following:

- Prohibited medication use
- Prohibited ART
- Non-compliance with study treatment

- Non-compliance with protocol procedures
- Other protocol deviation

The number and percentage of participants with important protocol deviations will be summarized by type of deviation for the Enrolled Set. Individual protocol deviations will also be presented in a list.

4.4 Demographics and Baseline Characteristics

Descriptive summaries of demographic and selected baseline characteristics will be presented for participants in the Safety Set. Demographic and baseline characteristics data will include:

- Age at informed consent, and the age categories as follows:
 - o 18 to <20 years
 - o 20 to <50 years
 - o ≥50 years
- Sex assigned at birth
- Gender identity at informed consent
- Child-bearing potential at informed consent, and
 - Pregnancy status at informed consent (when applicable)
- Race
- Ethnicity
- Height at baseline
- Weight at baseline
- Body mass index (BMI) and BMI categories at baseline as follows²
 - Severely Underweight: <16 kg/m²
 - o Underweight: 16 to <18 kg/m²
 - Normal Weight: 18 to <25 kg/m²
 - Overweight: 25 to <30 kg/m²
 - o Obesity Class I: 30 to <35 kg/m²
 - Obesity Class II: 35 to <40 kg/m²
 - o Obesity Class III: ≥40 kg/m²
- Vital signs at baseline
- History of tobacco use reported at baseline

A participant's age in years will be estimated using the year of informed consent and year of birth.

BMI will be calculated as (body weight in kilograms) / (height in meters)².

Participant demographics and baseline characteristics will also be presented in a listing.

4.5 Medical History

Medical history will be coded using the Medical Dictionary for Regulatory Activities (MedDRA) version 25.0 or higher. The number and percentage of participants by system organ class (SOC) and preferred term (PT) will be summarized.

Percentages will be calculated based on the number of participants in the Enrolled Set.

Participant medical history data, including specific details, will also be presented in a listing.

4.6 Prior and Concomitant Medications/Therapies, and Study Treatments

All medications will be coded according to the WHO Drug Dictionary version 2022 MAR or higher, and the GSK Drug Dictionary: Proprietary sponsor medication dictionary version 5.0 or higher.

A prior medication or ART will be defined as any medication/therapy that is taken or starts prior to the first dose of the study drug (whether stopped or continued after the first dose). A concomitant medication or ART will be defined as any medication/therapy taken on or after the date of first dose of study drug. Furthermore, a medication/therapy could be flagged as both a prior and concomitant medication if it was started prior to the first dose and continued after first dose of study medication.

4.6.1 Prohibited Medications

Prohibited medications, as described in the USPI include:

- Anticonvulsants: carbamazepine, oxcarbazepine, phenobarbital, phenytoin
- Antimycobacterials: rifabutin, rifampin, rifapentine
- Glucocorticoid (systemic): dexamethasone (more than a single-dose treatment)
- Herbal product: St John's wort (Hypericum perforatum)

Reported use of prohibited medications will be listed for the Enrolled Set.

4.6.2 Prior Medications or Antiretroviral Therapies

Prior medications/therapies will be summarized for participants in the Enrolled Set. The total number of prior medications/therapies, as well as the number and percentages of participants with at least one prior medication/therapy will be presented and listed by Anatomical Therapeutic Chemical level 1 classification and PT.

Prior medications/therapies will be presented in a listing.

4.6.3 Concomitant Medications or Antiretroviral Therapies

Concomitant medications/therapies will be summarized for participants in the Safety Set. The total number of concomitant medications/therapies, as well as the number and percentages of participants

with at least one concomitant medication/therapies, will be presented and listed by Anatomical Therapeutic Chemical level 1 classification and PT.

Concomitant medications/therapies will be presented in a listing.

4.6.4 Study Treatment Initiation Method

Study treatment initiation methods as described in the protocol include the following:

- Have been taking oral CAB + RPV or other ART for approximately 1 month (at least 28 days) prior to Baseline/Month 1, or
- Had already been receiving CABENUVA prior to Baseline/Month 1 and the last injections were within a 1-month \pm 7-day window or for every-2-month injections, the timing will vary they are receiving the initiation injections (1 month \pm 7 days) or the continuation injections (2 months \pm 7 days) per the USPI, or
- Had been prescribed direct to inject and received first injection without an oral lead-in at the IC/ASA on the last day of any other ART.

Initiation methods will be summarized and listed for all participants in the Safety Set.

4.6.5 Study Treatments

4.6.5.1 Duration of Exposure

Duration of exposure will be defined as the total number of days a participant is exposed to CABENUVA and will be presented as the total number of days from the first dose date to the last dose date (date of last dose minus the date of first dose + 1) as recorded for study discontinuation. If the last dose date for study discontinuation is not reported, the last available visit date or when lost to follow-up, the date of last contact will be used. For participants receiving CABENUVA prior to enrolling in the study, exposure will be counted from the date that therapy was initiated (which would predate study entry).

Because missed doses may occur during the study, exposure to the study drug will also be characterized by cumulative dose, which will be defined as the cumulative dose of CABENUVA injections administered to the participants.

A summary of each participant's exposure will be presented in a listing.

4.7 Analysis of Clinical Study Endpoints

4.7.1 Safety Analysis

All safety analyses will be presented for participants in the Safety Set.

The seriousness of an AE will be independently assessed by the investigator from the severity of the AE. An SAE will be defined as any untoward medical occurrence that at any dose results in death, is lifethreatening, results in a congenital anomaly/birth defect, requires in-patient hospitalization or prolongation, or results in significant disability/incapacity. Important medical events that may not result in death, be life-threatening, or require hospitalization may be considered SAEs when, based upon medical judgment, they may jeopardize the participant and may require medical or surgical intervention to prevent one of the outcomes listed above. All SAEs will be presented in a table with the number and percentage of participants who experienced the event. The summary table will be displayed by SOC and PT.

Similarly, the following types of AE will be summarized in separate tables, if applicable:

- Baseline AEs reported at the Baseline/Month 1 visit beginning before informed consent and during the oral lead-in/injections that are considered related to oral CAB + RPV or the last CABENUVA injection
- Treatment-related AEs
- AEs leading to discontinuation
- Injection site reactions

- Cardiovascular events
- Liver monitoring/stopping events
- Pregnancy-related AEs
- COVID-19-related AEs

Other non-serious AEs that are considered not related to CABENUVA or do not lead to withdrawal are not documented in the eCRF, and therefore will not be summarized.

4.7.1.1.1 Baseline AEs

For participants taking CABENUVA prior to enrollment in the study, any previous AEs related to oral CAB + RPV lead in or previous injection beginning before informed consent will be recorded and reported separately from events occurring during the study.

4.7.1.1.2 Treatment-related AEs

AEs that are considered related to study treatment will be summarized in separate tables.

4.7.1.1.3 Adverse Events Leading to Discontinuation

AEs that are associated with discontinuation of treatment will be summarized in separate tables and listings.

4.7.1.1.4 Injection Site Reactions

Injections site reactions, such as redness, itching, pain or swelling or discomfort, will be recorded and summarized in a table as well as in listings.

4.7.1.1.5 Cardiovascular Event Status

Type of event and specific event characteristics for arrhythmias, congestive heart failure, stroke/transient ischemic attack, deep vein thrombosis/pulmonary embolism, myocardial infarction, peripheral arterial thromboembolism, pulmonary hypertension, revascularization, and valvulopathy will be collected and reported.

Participants may have a standard 12-lead electrocardiogram (ECG) performed during the study as clinically indicated for a cardiovascular event. ECG overall interpretation will be summarized. ECG data (e.g., result, significance, abnormalities present) will be presented in a listing.

4.7.1.1.6 Liver Monitoring / Stopping Events

Start and stopping dates/times of liver events, any available liver labs, imaging, and/or biopsies, and patient exposures near the time of the event will be recorded and summarized. Alcohol intake at onset of liver events will be presented in a table for participants in the Safety Set.

4.7.1.1.7 Pregnancy Status at Baseline and Pregnancy-related Adverse Events

Child-bearing potential and pregnancy status at baseline will be reported as part of baseline information in a table. Individuals who become pregnant over the course of the study will be reported in a separate

listing. Any participant who becomes pregnant while participating in the study will be assessed by their HIV care provider whether to continue or discontinue CABENUVA and whether to remain in the study.

While pregnancy characteristics and outcomes are not part of the study nor documented within the eCRF, the reported occurrence of pregnancy during the study will be reported to the sponsor within 24 hours of awareness. All pregnancies will then be followed up by Sponsor until outcome (including premature terminations and complications) for both mother and child. Pregnancy information will be collected by the Sponsor from Day 1 and followed for 52 weeks, including any post-study SAEs possibly related to CABENUVA.

Pregnancy-related AEs (pregnancy complications, elective termination for medical reasons, spontaneous abortion, fetal death, stillbirth, congenital anomalies, ectopic pregnancy) will be captured in the AE form and reported in a separate listing.

4.7.1.1.8 COVID-19-related Adverse Events

Any AEs that are also coded with a COVID-19 infection will be reported in a separate table and listing.

4.7.1.1.9 Serious Post-injection Reactions

Any serious post-injection reactions, including dyspnea, agitation, abdominal cramping, flushing, sweating, oral numbness, and changes in blood pressure, will be recorded and will be presented in a listing.

4.7.2 Clinical Laboratory Assessments

Clinical laboratory values performed by local laboratories will be assessed at planned study visits. A summary table will present the count and percentage of subjects who have an abnormal value at each visit and overall.

When there are multiple values within a planned visit for a particular laboratory assessment, the observation closest to the analysis visit target study day should be used. If there are multiple assessments equidistant from the target study day, then the mean of these values will be used.

HIV-1 RNA and liver chemistries will be summarized. In addition, given adequate sample sizes, other lab assessments may be summarized to include:

- Hematology
- Chemistry
- CD4

Liver laboratory tests will be included with chemistry lab tests.

Summaries of hepatobiliary laboratory events including possible Hy's law cases will be provided. Possible Hy's law cases are defined as any elevated ALT $\geq 3 \times$ upper limit of normal (ULN), total bilirubin $\geq 2 \times$ ULN, and ALP <2 × ULN/missing. Total bilirubin $\geq 2 \times$ ULN can be within 28 days following the ALT elevation and if direct bilirubin is available on the same day, it must be $\geq 35\%$ of total bilirubin. ALP <2 × ULN/missing

means it is satisfied unless the ALP is $\ge 2 \times ULN$ at the time of bilirubin elevation. The summary will be produced for worst-case post-baseline only.

In addition to liver chemistries, liver biopsy and imaging will also be presented in a listing.

Harmonization of Local Laboratory Values

Harmonization of local laboratory value has been referenced in various publications due to differences in the test measurements. Normal laboratory reference interval values vary based on several factors, including the demographics of the healthy population from which specimens were obtained and the specific methods and/or instruments used to assay these specimens. Laboratories that are accredited by the College of American Pathologists are required to establish and/or validate their own reference values. Thus, any given result should be interpreted based on the reference value of the laboratory in which the test was done. This study will receive the results from different laboratory centers. Therefore, the laboratory results should be interpreted based on the reference value of the laboratory in which the test was done since there is no central laboratory involved.

4.7.3 Changes in Vital Signs

Summary tables presenting observed values and changes from baseline for each visit will be presented for vital sign data, including systolic/diastolic blood pressure (mmHg), heart rate (beats/min), as well as height (cm), weight (kg), and BMI (kg/m²). Vital signs will be assessed in a semi-supine position.

Vital signs, height, weight, and BMI will be presented in a listing.

4.7.4 Effectiveness

A summary of HIV-1 RNA results per visit will be provided. If HIV-1 RNA data is documented at unscheduled or early withdrawal visits, the data will be assigned to the closest scheduled visit. However, if data from a scheduled visit is already available from the same timepoint, this data is prioritized and data from the unscheduled/early withdrawal visit will not be used for analysis. All documented data on HIV-1 RNA (at scheduled and unscheduled visits) will be presented in the listings.

The number and percentage classified as virologically suppressed and confirmed virologic failure will as be reported as defined below.

Virological Suppression

Virological suppression will be defined as observing plasma HIV-1 RNA <50 copies/mL.

The proportion of participants with virologic suppression will be summarized using the Safety Set. 95% CIs will be calculated using Clopper-Pearson exact CI as appropriate for large and small sample sizes.

Confirmed Virologic Failure

Confirmed virologic failure will be defined as observing two consecutive plasma HIV-1 RNA ≥200 copies/mL.

The proportion of participants with confirmed virologic failure will be summarized using the Safety Set. 95% CIs will be calculated using Clopper-Pearson exact CI.

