# 4.3. Study Groups and Duration

This study will include the following groups: An Expert Panel, HIV care providers, virologically suppressed PLWHIV seeking to start or continue CABENUVA for treatment for HIV-1, and the IC/ASA staff. A CABENUVA POT will be agreed between the HIV care provider and the IC/ASA prior to study participants receiving their first study related injections at the IC/ASA.

Assessments can be found in Annex 1: Schedule of Activities and in the POT.

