#### **ANNEX 1: SCHEDULE OF ACTIVITIES**

Procedure 	Baseline/			Treatme	ent Period (	Months)			E.D. 	Notes
riocedure	Month 1 	2	3	4	5	6	7	8	L.D.	Notes

- 1. The timing and number of planned study assessments may be altered during the study based on newly available data.
- 2. The following sequence of events must be followed for participants at the Baseline/Month 1 visit: 1) Informed consent form (ICF) Consent 2) Confirm Inclusion and Exclusion criteria 3) complete questionnaires and assessments, 4) Receive first study related intramuscular (IM) injections at the IC/ASA. Baseline is defined as the Month 1 visit.
- 3. E.D = early discontinuation/ withdrawal: This visit should only be conducted if the participant discontinues from the study, and the discontinuation/withdrawal reason should be recorded.

NOTE: Carefully follow the Instructions for Use when preparing and administering CABENUVA IM to avoid accidental intravenous administration

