#### **Clinical and Other Assessments**

Informed consent	Х									Written informed consent must be obtained from each potentially eligible participant by IC/ASA personnel prior to the initiation of any Baseline procedures as outlined in this protocol.
Inclusion and exclusion criteria	Х									Inclusion/exclusion criteria will be fully assessed at the Baseline/Month 1 Visit.
Demography	Х									
Pregnancy Status	X	x	X	X	X	X	X	X	Х	Ask POCBP at each visit if they are pregnant and ask for the date of their LMP. See Section 10.3.11 for additional information.
Tregnancy Status	^	^	^	^	^	^	^	^	^	For participants on every 2 monthly injections, pregnancy status should be confirmed only at IC/ASA visits

Due se dune1	Baseline/			Treatme	ent Period (	Months)			ED3	Notes
Procedure 	Month 1 	2	3	4	5	6	7	8	E.D.3	Nutes
										Height will only be collected at Baseline. BMI will be calculated within the eCRF.
Height and weight	Х	Х	X	Х	Х	Х	Х	Х	X	If possible, the same scale should be used consistently throughout the study and participants should be asked to remove any excess clothing (i.e., coats and shoes).
										For participants on every 2 monthly injections, weight would be collected only at IC/ASA visits
Vital signs: blood pressure, heart rate	X				ording to the the particip					Vital signs are to be measured after resting in a semi-supine position for at least 5 minutes.  For participants on every 2 monthly injections, vital
										signs would be collected only at IC/ASA visits  The Baseline/Month 1 labs should be collected
Laboratory								Х	_	prior to the first study injection (at the Baseline/Month 1 visit. See Section 10.1 for additional information
assessments (HIV1- RNA, liver chemistries, other labs per POT)	X	the HI	V care provi s	der. All lab ource docui	y be obtaine reports mus mentation a otherwise r	st be stored t the IC/ASA	in the parti A.	cipants	х	The HIV care provider is responsible for monitoring and any follow-up of elevated HIV-1 RNA and liver chemistries in their PLWHIV and to let the IC/ASA know if there are any changes to the monthly or every 2-month injections. The HIV care provider can request that the IC/ASA draw labs at any time or they can perform local labs as required.
Study Treatment: All	injections wi	ll be admin	istered acc	ording to t	he CABENI	JVA USPI.				

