7.1 Schedule of Activities (SoA)

Procedure ¹	Baseline/ Month 1 ²		Treatment Period (Months)							
		2	3	4	5	6	7	8		

- The timing and number of planned study assessments may be altered during the study based on newly available data.
- 2. The following sequence of events must be followed for participants at the Baseline/Month 1 visit: 1) informed consent form (ICF) Consent 2) confirm inclusion and exclusion criteria 3) complete questionnaires and assessments, 4) receive first study-related intramuscular (IM) injections at the IC/ASA. Baseline is defined as the Month 1 visit.
- 3. E.D. = early discontinuation/withdrawal: This visit should only be conducted if the participant discontinues from the study, and the discontinuation/withdrawal reason should be recorded.

NOTE: Carefully follow the Instructions for Use when preparing and administering CABENUVA IM to avoid accidental intravenous administration

Clinical and Other Assessments

Clinical and Other Assessments										
Informed Consent	X									Written informed consent must be obtained from each potentially eligible participant by IC/ASA personnel prior to the initiation of any Baseline procedures as outlined in this protocol.
Inclusion and Exclusion Criteria	Х									Inclusion/exclusion criteria will be fully assessed at the Baseline/Month 1 Visit.
Demography	Χ									
Pregnancy Status	Х	Х	X	X	Х	Х	X	X	Х	Ask POCBP at each visit if they are pregnant and ask for the date of their LMP. See Protocol Section 10.3.11 for additional information. For participants on every-2-month injections, pregnancy status should be confirmed only at IC/ASA visits.
Height and Weight	Х	Х	Х	Х	Х	Х	Х	Х	X	Height will only be collected at Baseline. BMI will be calculated within the eCRF. If possible, the same scale should be used consistently throughout the study and participants should be asked to remove any excess clothing (i.e., coats and shoes).

										For participants on every-2-month injections, weight will be collected only at IC/ASA visits.
Vital Signs: Blood Pressure, Heart Rate	X				ording to the din the par		Vital signs are to be measured after resting in a semi-supine position for at least 5 minutes. For participants on every-2-month injections, vital signs will be collected only at IC/ASA visits.			
Laboratory								Х		The Baseline/Month 1 labs should be collected prior to the first study injection (at the Baseline/Month 1 visit). See Section 10.1 for additional information

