Assessments (HIV1- RNA, Liver Chemistries, Other Labs Per POT)	Х	the HIV	care provid	der. All lab source do	be obtained reports must cumentation otherwise r	Х	The HIV care provider is responsible for monitoring and any follow-up of elevated HIV-1 RNA and liver chemistries in their PLWHIV and tet the IC/ASA know if there are any changes to the monthly or every-2-month injections. The F-care provider can request that the IC/ASA draw labs at any time or they can perform local labs a required.			
Study Treatment: All inj	ections will be	e administer	ed accordin	g to the CA	ABENUVA US	SPI				
CABENUVA IM Injection	s initiated at		The final oral doses of CAB + RPV, or other ART, should be taken on the same day when injections with CABENUVA are started. Questionnaires and procedures should be conducted prior to the injections.							
Monthly Dosing (Post Oral Lead-In)	X	Х	Х	Х	X	Х	Х	Х		IM dosing is expected to occur on the same date of the month as determined by Dose 1 - Treatment Target Date. Dosing window is ±7 days.
Every-2-month Dosing	Х	Х		Χ		Х		Х		Dosing window for every-2-months is \pm 7 days.
CABENUVA IM Continua subsequent injections a	•		already red	ceiving CAB	BENUVA inje	ections, and	who are to	get their		Questionnaires and interviews should be conducted prior to the injections.

Note: To avoid having participants whose last injections are at Month 7 return to the IC/ASA at Month 8, the end of study assessments (Month 8) will be completed at Month 7. Questionnaires and potential interviews will be completed at Month 8.										
Monthly Dosing	Х	X	X	Х	Х	Х	X	Х		The first study-related CABENUVA injections at the IC/ASA should be started within 1 month (±7 days) after the last injections. For participants switching from an every-2-month continuation injection schedule to a monthly continuation dosing schedule, follow the dosing instructions in the most recent USPI for CABENUVA.
Every-2-month Dosing (Participants Already Receiving Every-2-month Dosing)	X		X		Х		X			Dosing window for every-2-month dosing is ±7 days. For participants switching from a monthly continuation injection schedule to an every-2-month continuation injection dosing schedule follow the dosing instructions in the most recent USPI for CABENUVA.

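### Confirmed virologic failure needs two consecutive HIV-1 RNA values, but only one post-baseline sample is fixed and the SAP's visit rules can discard the confirming retest, so on-study failure is under-counted to an unknown degree

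*SAP*

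**What the plan says.** Clinical SAP 4.7.4 (Effectiveness) gives the rule: "Confirmed virologic failure will be defined as observing two consecutive plasma HIV-1 RNA ≥200 copies/mL". It does not say whether the baseline value may be the first of the pair, how far apart the two values may lie, or how a participant with fewer than two values is counted. On the denominator it says: "The proportion of participants with confirmed virologic failure will be summarized using the Safety Set". The interval is Clopper-Pearson. Suppression is defined separately as below 50 copies/mL.

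The sampling is set in the schedule of activities (Protocol Annex 1, repeated in clinical SAP 7.1). The laboratory row, "Assessments (HIV1- RNA, Liver Chemistries, Other Labs Per POT", is marked at Baseline/Month 1, Month 8 and early discontinuation. Three notes matter:

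- Baseline precedes on-study treatment: "The Baseline/Month 1 labs should be collected prior to the first study injection".
- Early discontinuation takes the place of Month 8. Annex 1 says: "This visit should only be conducted if the participant discontinues from the study".
- For participants whose last injections fall at Month 7, the end-of-study "assessments (Month 8) will be completed at Month 7", which moves the final sample without adding one.

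Between these points testing is discretionary. Annex 1 says: "The HIV care provider can request that the IC/ASA draw labs at any time or they can perform local labs as required". Protocol 5.1.1 and 10.1 also let the Expert Panel, the blueprint and the POT set required labs and their timing. Protocol 4.3 describes the participants as "virologically suppressed PLWHIV seeking to start or continue CABENUVA for treatment for HIV-1".

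Two SAP rules govern extra values. Under 4.7.4, an unscheduled or early-withdrawal HIV-1 RNA result goes to the nearest scheduled visit, but is left out of the analysis if that visit already has a scheduled result. Under 4.7.2, several results within one planned visit are reduced to the one nearest the target day, or to the mean if they are equally near.

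**The concern.** A definition that needs two consecutive values needs two chances to observe them. The fixed schedule offers one after baseline. A participant who enters suppressed and rebounds is first seen at the final sample. Participation then ends, so no later study visit can confirm the rebound, and the participant stays in the denominator as a non-failure.

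The fixed-visit pair that can qualify begins with a sample drawn before the first study injection, so it says little about failure arising during care at the infusion center. Where a provider does order a prompt retest, the two visit rules may remove it.

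At stake is how the failure proportion and its interval are read. They would look like evidence that failure is rare at these sites, when part of the denominator may have had no opportunity to meet the definition.

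**Working it through.** The documents state no expected failure rate, evaluable number or power for this endpoint, so there is no planned figure to reproduce.

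**Step 1. Count fixed samples.** Each participant has one baseline sample and one post-baseline sample (Month 8, or Month 7, or early discontinuation). The only consecutive pair on fixed visits is baseline and final. A participant below 200 copies/mL at baseline therefore has probability 0 of being classed as failing, whatever the final value.

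**Step 2. Follow a retest.** Suppose the Month 8 value is 200 or more and a repeat is drawn soon after. Its nearest scheduled visit is Month 8, which already has a scheduled value, so under 4.7.4 the repeat is not used. Under 4.7.2, two results within the planned visit become one. Read literally, a prompt confirmation can disappear.

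**Step 3. Write the observed rate.** All four parameters are assumptions, shown as ranges:

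- q: proportion with baseline HIV-1 RNA of 200 or more
- k: share of those still at 200 or more at the final sample
- r: true on-study failure rate among the others
- c: share of those failures with two consecutive analysable values

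Observed rate = q·k + (1 − q)·r·c.

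With q = 0 and N = 120 (the maximum enrolment), the observed rate and expected count are:

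| True r | c = 0 | c = 0.25 | c = 0.5 | c = 1 |
|---|---|---|---|---|
| 1% | 0% (0) | 0.25% (0.3) | 0.5% (0.6) | 1.0% (1.2) |
| 3% | 0% (0) | 0.75% (0.9) | 1.5% (1.8) | 3.0% (3.6) |
| 5% | 0% (0) | 1.25% (1.5) | 2.5% (3.0) | 5.0% (6.0) |

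Fixed samples alone mean c = 0, and the table then prints zero whether the true rate is 1%, 3% or 5%. If q is 1% to 2% and k is 0.25 to 1, fixed samples alone give q·k = 0.25% to 2.0% (0.3 to 2.4 participants), again regardless of r.

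The chance of at least one confirmed failure is 1 − (1 − r·c)^120. At r = 3% and q = 0 it is 0 for c = 0, 0.84 for c = 0.5 and 0.97 for c = 1.

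**Step 4. Intervals.** The Clopper-Pearson upper limit for 0/n is 1 − 0.025^(1/n):

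- 0/120: 0 to 3.0%
- 0/80: 0 to 4.5%
- 0/30: 0 to 11.6%

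For 3/120 (2.5%) the exact interval is about 0.5% to 7.1%. The 80, 30 and 3/120 cases are illustrations. They show how far the printed 3.0% depends on treating every treated participant as evaluable, and what three unconfirmed final values of 200 or more would look like.

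**The case against.** The strongest reply is that the analysis is not confined to fixed visits. Providers may order tests at any time, viral loads obtained outside study visits go into the eCRF (Protocol 4.3.3), and 4.7.4 admits unscheduled values where no scheduled one exists. The blueprint and POT are stand-alone documents (Protocol Annex 2) and may have required interim HIV-1 RNA. This stands. A reader might infer that a near-zero rate is built in; the documents do not support that, because c is unknown and need not be small. Nor do they support saying that most of the denominator could never have met the definition, since no count of participants with two post-baseline values is given.

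A reader might also infer that an unconfirmed final value of 200 or more is reported nowhere. That is not so: all documented values are listed (Listing 16.3.14) and Table 14.2.1 summarises HIV-1 RNA over time. Whether that table separates 50 to 199 from 200 and above cannot be seen, because the shells are an attachment. What is missing from 4.7.4 is a defined proportion for such values.

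A simple repair would be to require both values to be post-baseline. That goes too far. Some participants are already on CABENUVA at entry (Protocol 4.2.1.1), so a high baseline value can be viraemia on treatment, and the restriction would leave no qualifying pair on fixed visits.

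Finally, the endpoint is tertiary, descriptive and unpowered (clinical SAP 1 and 4.1.4), and the tertiary objectives are redacted, so the protocol's wording for it cannot be checked. This limits the weight of the point. It does not answer the visit rules or the denominator.

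**Conclusion.** The point holds as a matter of ascertainment. On fixed visits nobody suppressed at baseline can be classed as a confirmed failure. Beyond them, detection rests on testing of unknown frequency, filtered by rules that can discard the confirming value. On-study failure is therefore under-counted by the factor c in the calculation above: from nothing lost (c = 1) to everything lost (c = 0) among participants suppressed at baseline. The documents do not allow c to be estimated.

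The Safety Set interval, 0 to 3.0% for 0/120, reflects sampling error only and counts unevaluable participants as non-failures. This reading assumes that the 4.7.2 and 4.7.4 visit rules apply to the failure derivation as well as to the per-visit summaries; the SAP does not say otherwise. The primary endpoint, the Feasibility of Intervention Measure (FIM) at Month 8, is unaffected. This is a cheap improvement, not a flaw in the main analysis.

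**What to change.** Amend clinical SAP 4.7.4, with no new sampling and no change to clinical management:

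1. Derive confirmed failure from all documented HIV-1 RNA values in date order, not from visit-mapped values.
2. Add the number and percentage whose last on-study HIV-1 RNA is 200 copies/mL or more, confirmed or not.
3. Beside the Safety Set figure, report how many participants had at least two post-baseline results, and the confirmed-failure proportion on that denominator.
4. Show separately any confirmed failure whose first value is the baseline sample.

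The cost is SAP wording and a few table rows from data already collected. The drawback is a failure figure that may be less favourable or less precise. The group with two or more post-baseline results may also be selected, because providers are likely to retest those they worry about, so items 2 and 3 should be read together with the Safety Set figure and not in place of it.
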